## **Background and objectives**

The PAPAartis trial was established to test the hypothesis that MISACE can greatly reduce the incidence of ischaemic spinal cord injury (SCI) and mortality compared to standard open surgical or endovascular thoracoabdominal aneurysm repair alone for adult patients requiring thoracoabdominal aortic aneurysm repair (TAAA), Crawford type II or III(1). The health economic analysis will compare mean costs and QALY outcomes of MISACE versus standard procedures.

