### ***Within study economic analysis***

The base-case health economic analysis will be a within-study cost-utility analysis. The analysis will take a one year time horizon.

The clinical study is collecting EQ-5D at baseline and 1 year, time in surgery, intensive care and hospital, resource use for staff and consumables during the procedures and during the hospital stay, impact on kidney function, and use of rehabilitation and other healthcare after discharge from hospital.

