### ***Missing data***

A common methodological problem in within-trial cost effectiveness analyses is missing data. Costs for each patient are “composite” variables, that is, they are the unit-cost weighted sum of several resource use items, collected at different time points. If even one of these items is missing in a patient’s record, the total cost for that patient cannot be computed. A similar problem can occur for the calculation of QALYs, which are composite variables calculated as the “area under the curve” of HRQOL observations taken at different time points. Hence we conducted a methodological review of methods for handling missing data in within-trial economic evaluations, and developed code in STATA and R to implement those methods in the PAPAartis study. The study found that multiple imputation with predictive mean matching was likely to offer a flexible and robust approach (6), though results are sensitive to the method chosen and so sensitivity analyses should be conducted using alternative methods.

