### ***Interventions and Comparators***

The intervention is MISACE, followed by open repair or endovascular repair according to the clinician's choice. The standard procedures are open repair or endovascular repair according to the clinician's choice, without MISACE.

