### ***Uncertainty***

Scenario analyses will be used to estimate the costs and QALY in the one-year time horizon using estimates of EQ-5D tariffs from other countries and a range of unit costs. Different methods for handling missing data will be used. Bootstrapping will be used to estimate confidence intervals for incremental cost and QALY and cost-effectiveness acceptability curves (CEAC).

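### With EQ-5D measured only at baseline and 1 year, baseline utility is half of a survivor's QALY, yet the plan names no baseline adjustment for incremental QALYs

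*Protocol*

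**What the plan says.** - Protocol, Background and objectives: "The health economic analysis will compare mean costs and QALY outcomes of" MIS2ACE and the standard procedures.
- Protocol, Within study economic analysis: "The clinical study is collecting EQ-5D at baseline and 1 year", and "The analysis will take a one year time horizon".
- Protocol, Missing data: QALYs are the area under the curve "of HRQOL observations taken at different time points".
- Protocol, Uncertainty: "Bootstrapping will be used to estimate confidence intervals for incremental cost and QALY", with acceptability curves. The scenarios cover EQ-5D tariffs from other countries and a range of unit costs, and "Different methods for handling missing data will be used".

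No section names a covariate for the QALY comparison, and none says that the comparison is unadjusted. The Protocol refers to the Statistical Analysis Plan only for the analysis population (Study population). It does not defer the QALY estimator to it.

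**The concern.** Half of the outcome for a patient alive at 1 year is a value measured before treatment. If the arms differ by chance at baseline, part of that difference appears as incremental QALYs and carries into the acceptability curve. The baseline value also adds variance that treatment cannot influence and that regression could remove.

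An analyst who follows the document as written would bootstrap a difference in mean QALYs. Because the text is silent, the choice between an adjusted and an unadjusted estimate would also be open after the data are seen.

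**Working it through.** The document states no sample size, SD, correlation or expected QALY difference, so there is no figure of its own to reproduce.

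**Inputs from the Protocol.** Two EQ-5D points one year apart, an area-under-the-curve QALY, and a one-year horizon. Table 2 gives 1-year mortality from one published study: 31.6% endovascular and 21.5% open.

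**Assumptions, not from the Protocol.** Correlation rho between baseline and 1-year utility 0.2 to 0.7; ratio k of the 1-year to the baseline SD 1 to 2; deaths 10% to 30%. For the simulation with deaths: rho 0.3 to 0.5, both SDs 0.20, means 0.80 and 0.75, death unrelated to baseline utility and falling either within 30 days or uniformly over the year, and utility declining linearly to zero at death.

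**1. Weight of baseline.** For a patient alive at 1 year, Q = 0.5·U0 + 0.5·U1. The weight of U0 is one half. It is smaller for patients who die.

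**2. Pass-through of an imbalance among survivors.** The slope of Q on U0 is 0.5·(1 + rho·k). With k = 1:
- rho = 0.3: 0.65
- rho = 0.5: 0.75
- rho = 0.7: 0.85

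An assumed baseline difference of 0.03 adds 0.5 × 0.03 = 0.015 QALY directly. Counting the correlation with the 1-year value, the shift is 0.0195, 0.0225 or 0.0255 QALY. A wider spread at 1 year raises the slope (k = 2, rho = 0.5: 1.00).

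**3. Size of chance imbalance.** Assume an EQ-5D SD of 0.22. The standard error of the direct half-weight part is 0.5 × 0.22 × √(2/n):
- n = 75 per arm: 0.018 QALY
- n = 150 per arm: 0.013 QALY
- n = 250 per arm: 0.010 QALY

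**4. Precision among survivors.** R² = (1 + rho·k)² / (1 + k² + 2·rho·k), and the ratio of adjusted to unadjusted SE is √(1 − R²).
- k = 1, rho = 0.5: R² = 2.25/3.00 = 0.75, ratio 0.50
- k = 1, rho = 0.3: R² = 1.69/2.60 = 0.65, ratio 0.59
- k = 1, rho = 0.7: R² = 0.85, ratio 0.39
- k = 2, rho = 0.2: R² = 1.96/5.80 = 0.338, ratio 0.81

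For k = 1 the variance ratio simplifies to (1 − rho)/2.

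**5. With deaths included** (simulation, k = 1, rho 0.3 to 0.5, both death timings):

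| Deaths | Slope of Q on U0 | SE ratio, adjusted to unadjusted |
|---|---|---|
| 10% | 0.59 to 0.70 | 0.82 to 0.90 |
| 20% | 0.53 to 0.65 | 0.89 to 0.95 |
| 30% | 0.46 to 0.60 | 0.92 to 0.97 |

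Deaths add QALY variance that baseline utility does not explain, so the gain shrinks as mortality rises. The extreme R² values are 0.062 and 0.335. They correspond to 1/(1 − 0.062) = 1.07 and 1/(1 − 0.335) = 1.50, so an unadjusted analysis would need about 7% to 50% more patients for the same precision.

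**6. Bias.** Over 20,000 simulated trials (survivors only, 75 per arm, rho = 0.5), the mean unadjusted difference under no effect was 0.0001. Its SD was 0.0283, against 0.0143 after adjustment. The unadjusted estimator is unbiased on average; the error is conditional on the imbalance that occurs.

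**The case against.** The strongest reply is that the document never says the comparison is unadjusted. The objective is one sentence, comparing mean QALYs is compatible with regression-adjusted means, and a bootstrap gives intervals around whatever estimator is chosen. Covariates are often listed in a statistical analysis plan, which is not shown here. This stands in part: a reader might infer that the plan fixes a raw estimator, and the text does not support that. But the document is itself the economic analysis plan. It specifies the tariff, perspective, imputation approach, bootstrap, scenarios and discount rate, and it looks to the Statistical Analysis Plan only for the population. The omission is therefore a fair point on this document.

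The second reply is that randomisation makes the unadjusted difference unbiased and that the gain is modest in the full analysis set. Both are correct. At 20% to 30% deaths, close to the mortality in Table 2, the standard error falls by only 3% to 11%. That limits the benefit, but the covariate is already collected.

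A reader might also extend the point to costs, because repair type is the clinician's choice in both arms and Table 4 prices stent grafts far above open grafts. The documents do not support a claim that imbalance in repair mix would swamp the cost of MIS2ACE:
- the 80000 euro price is one centre's ceiling;
- coil prices are given but not the number of coils, so the cost of MIS2ACE cannot be computed;
- longer stays after open repair would offset part of the device gap;
- neither the randomisation scheme nor a pre-allocation record of intended repair is described;
- baseline EQ-5D is not a component of cost.

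**Conclusion.** The point holds for QALYs, as an improvement that should be made and not as an error that invalidates the analysis. Under the assumptions shown, about 46% to 70% of a chance baseline imbalance reaches the incremental QALY when 10% to 30% of patients die. Adjustment brings the standard error to about 0.82 to 0.97 of the unadjusted value. Among survivors the ratio is 0.39 to 0.81 over the wider range of rho and k, but that is not the planned population.

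Three stronger readings go beyond the documents:
- that baseline imbalance passes in full into the result: the direct weight is one half for survivors, and the total depends on a correlation and SDs that are not given;
- that the incremental QALY is systematically biased: it is not, over repeated randomisation;
- that the imbalance rivals the treatment effect: no expected QALY difference is stated to compare it with.

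The structural facts (two time points, area under the curve, no adjustment named) come from the text. The sizes depend on the assumed correlation, equal SDs at the two times, and deaths unrelated to baseline utility.

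**What to change.** Add to the Uncertainty section of the Protocol, before results are seen: incremental QALYs are estimated by linear regression on arm and baseline EQ-5D utility, plus any randomisation stratification factors. The regression is run within each bootstrap and imputation replicate, so that the intervals and the acceptability curve reflect it. Unadjusted mean QALYs are reported as a sensitivity analysis. In the tariff scenarios, value the baseline covariate with the same tariff as the outcome.

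The cost is one or two sentences and a small change in code; baseline EQ-5D is already collected. If the Statistical Analysis Plan already specifies this, a cross-reference is enough. Adjusting costs for intended repair type is optional. It applies only if that intention was recorded before allocation; the repair actually received should not be used, because it is determined after randomisation.

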## **Literature reviews**

A systematic literature review was undertaken in October 2019 to identify publications including cost analyses or health economic analyses of procedures for repair of complex abdominal aortic aneurysms(2). The purpose of the review was to develop a framework for the health economic analyses and identify modelling approaches. 4 studies were identified. Populations and treatments were heterogeneous. One was a protocol paper without results, one was a Markov model, one was a decision tree and one was a within trial analysis (Table 1). The time horizon varied from 30 days to lifetime.

**Table 1. Characteristics of the included studies (reproduced from (2))**

Authors, price year	Country	Population	Treatment compared	Discount rate (%)	Model used	Time Horizon	Effectiveness measure
Cianí 2017	UK	CAAA	f EI vs SI	Yes	Markov	10 years	QALY
Michel 2015	France	JRAAA or TAAAs	f/b EI vs SI	No	n/a	30 days	Clinical outcomes
Armstrong 2014	UK	JRAAAAs or TAAAs	f/b EI vs SI y f EI vs M	n/a	n/a	n/a	n/a
Vaislic 2009	USA	Type II & III TAAAs	EI vs SI	No	Decision tree	30 day, 1yr and lifetime	Clinical outcomes

CAAA = Complex abdominal aortic aneurysm. TAAAs = Thoracoabdominal aortic aneurysms. JRAAAs = Juxtarenal abdominal aortic aneurysms. f / b EI = Fenestrated / branched endovascular intervention. EI = Endovascular intervention. SI = Open surgical intervention. QALY = Quality-adjusted life year. M medical treatment only. IC = incremental cost. N/a reported a protocol for a study but no results

In terms of clinical outcomes, all studies reported 30 day mortality. 2 studies considered spinal cord injury outcomes, one included the risk of permanent kidney damage and hemodialysis, and one study considered the risk of re-interventions beyond 30 days (Table 2).

Table 2. Clinical outcomes and complications reported (reproduced from (2))

	Cianí et al.		Michel et al.		Vaisilic et al.	
	EI	SI	EI	SI	EI	SI
30 day mortality	2.6%	14%	6.7%	5.4%	7.9%	14.9%
1 yr mortality	n/a		n/a		31.6%	21.5%
Paraplegia or SCI	n/a		4.1%	1%	10.5%	15.7%
Permanent Hemodialysis	n/a		5.6%	17.2%	n/a	
<30 day re-interventions	7%	3%	9.1%	5.6%	n/a	
>30 day re-interventions	0.088/py	0	n/a		n/a	

EI = Endovascular intervention. SI = Surgical intervention. n/a = not reported. Py person year. Armstrong does not report any clinical complications in his study. SCI = Spinal cord injury.

3 of the 4 studies reported resource use in natural units (as well as in monetary values), as recommended by methods guidelines (3) (Table 3). All these 3 studies reported intensive care and hospital stay. 2 reported operating time and blood units, and one reported radioscopy time and use of contrast. One reported transfer to a rehabilitation centre after the hospital stay.

Table 3. Hospital resources consumed, units (reproduced from (2))

	Michel et al.		Cianí et al.		Armstrong et al.	
	SI	EI	EI	SI	EI	SI
ICU stays (days)	4	3.6	2.53	3.41	3.6	18.3
Operating time (min)			289.72	251	278	120
Duration of hospital stay (days)	16.2	13.9	5.17	10	7	14
Blood products, ml			360	1463	370	3436
Radioscopy (min)					71	
Contrast (ml)					222	
Transfer to rehabilitation	15.4%	5%				

ICU=intensive care units. Vaisilic et al. does not report an estimate of the resources consumed. n/a = not reported

One study estimated the lifetime costs of spinal cord injury as \$463,116 for the first year and \$61,550 for each year subsequently. However, this estimate was based on

data from a single US centre. This may not be generalizable to European settings, and the paper did not estimate the HRQOL of patients.

To address these questions, a second systematic literature review was undertaken to quantify the impact of SCI on health related quality of life and costs. 67 studies were included(4). Although there was considerable heterogeneity in terms of setting, perspective, study design and severity of disability, some general conclusions could be drawn. The estimated lifetime expenditure per individual with SCI ranged from \$0.5 million to \$2.0 million, with greater costs associated with earlier age at injury, neurological level, United States healthcare setting, and the inclusion of non-healthcare items in the study. HRQOL is negatively associated with neurological level of injury, particularly on mobility and physical dimensions. However, some studies indicate that mental health scores do not tend to be lower for people with more severe neurological injury. Furthermore, longitudinal studies show that most dimensions of QoL appear to improve over time, at least over the first year since the injury.

### **Unit costs**

Unit costs were requested from a survey of the participating centres in April and May 2022. The centre in Germany was able to provide detail about costs of tests (MRI, CT) and consumable items (coils, stent grafts etc.) but information about staff unit costs was considered confidential. The centre in Poland was able to give estimates of the cost of consumables and staff (Table 4). The data obtained from the survey were compared, where available, with national unit costs collected by NHS England (2021-22) and the Personal and Social Services Research Unit (PSSRU) in 2021. The unit costs for most consumable items in Poland and Germany seem to be within same range. The exception is the cost of an endovascular stent used in the aneurysm repair, which the German centre estimates may reach 80000€, depending on the complexity of the device. D’Oria et al. found the median cost of the stent graft and other central supplies to be \$17272 (interquartile range 8683-27931)(5). The cost of outpatient visit appears considerably greater in England than Germany or Poland. This may be because the unit costs for England can include office-based procedures. The cost per hour of medical professionals appears considerably greater in England. This may be because the data for England impute the cost of non-patient facing time (administration, training, management etc.) into the estimate. These differences in the estimates of unit costs will be considered in sensitivity analyses.

Table 4. Cost per item from the survey of centres, compared with published unit costs for England.

Items	Silesian Center for Heart Diseases in Zabrze, Poland, euros 2022	University Leipzig, euros 2022	NHS England 2021-22 reference costs, and PSSRU unit costs 2021, £
Outpatient visit	40	50	107-554 for a cardiothoracic OP visit, depending if first or follow up attendance and grade of physician.
Angio CT of arteries	160-161	120	40 - 293, depending on duration and use of contrast
Angio MRI of aorta	315		95-346 depending on number of areas and use of contrast
Cost per hour of staff			
Surgeon	28		31-123 depending on grade
Radiographer	33-44		37-147 depending on grade
Anaesthetist	33-44		31-123 depending on grade
MISACE items			
Coils	100	10 - 250	
Aneurysm repair items			
Wire	120		
Sheath	87		
Microcatheter	305		
Catheter	20		
Coil pusher	110		
Endovascular stent graft	7395	10000-80000	
Blood product pack	50		
Operating room per minute	5.84		
Cost per day in normal hospital bed	448		

Cost per day in intensive care	886		
Open repair graft	100-500		

### ***Within study economic analysis***

The base-case health economic analysis will be a within-study cost-utility analysis. The analysis will take a one year time horizon.

The clinical study is collecting EQ-5D at baseline and 1 year, time in surgery, intensive care and hospital, resource use for staff and consumables during the procedures and during the hospital stay, impact on kidney function, and use of rehabilitation and other healthcare after discharge from hospital.

### ***Missing data***

A common methodological problem in within-trial cost effectiveness analyses is missing data. Costs for each patient are “composite” variables, that is, they are the unit-cost weighted sum of several resource use items, collected at different time points. If even one of these items is missing in a patient’s record, the total cost for that patient cannot be computed. A similar problem can occur for the calculation of QALYs, which are composite variables calculated as the “area under the curve” of HRQOL observations taken at different time points. Hence we conducted a methodological review of methods for handling missing data in within-trial economic evaluations, and developed code in STATA and R to implement those methods in the PAPAartis study. The study found that multiple imputation with predictive mean matching was likely to offer a flexible and robust approach (6), though results are sensitive to the method chosen and so sensitivity analyses should be conducted using alternative methods.

### ***Unit costs***

Unit costs will be informed by the survey of centres, published studies(4,5,7,8), national unit cost tariffs and unit cost databases(9). For patients requiring haemodialysis, Lorenzo et al (2010)(7) estimated a detailed bottom-up microcosting study, and found that the mean cost per patient per year in Spain was 43234€ (SD 13932), of which 51% were the sessions, 27% medicines, 17% hospitalizations, 3% transport, and 2% ambulatory visits. Shukri et al (2022) found similar results in Germany: the mean cost of HD was 47501€ and the mean cost of PD was 46235€ (excluding transportation costs).

### ***Study population***

The population will concur with the full analysis set as stipulated in the Statistical Analysis Plan(1)

### ***Setting & location***

The PAPAartis study includes centres from several European countries with a focus on Germany (n=10), but also including one from each of Austria, France, Italy, the Netherlands, Poland, Sweden, Switzerland and the United Kingdom. The base case analysis will apply HRQOL tariffs for Germany(10).

### ***Use of real world data alongside randomised data***

The task envisaged the use of non-randomised registry data (European Registry of Endovascular Aortic Repair Complications, EuREC) to compare MIS2ACE versus standard care using non-randomised data. This task was originally planned because relatively few patients were anticipated as available to be recruited within the Randomised Controlled Trial, and the aim of the task was to take advantage of the registry data to complement the results emerging from the RCT.

However, shortly after beginning the PAPAartis project, and after commencing detailed discussions with the principal investigator of the registry ([name]) it became clear that the EuREC was unsuitable for the task originally planned. There were not sufficient variables collected in the Registry study to enable identification of Type II or III Crawford aneurysms, and hence identification of suitable controls in the registry data would be impossible.

At the same time, the PAPAartis investigators were successful in a bid to the German Research Foundation (DFG) to incorporate several more German and Austrian sites into the project, increasing the sample size and including patients with Type I, II and III aneurysm.

Hence it was decided by the PAPAartis investigators that the Registry data would not be necessary, as a reasonably large sample size would be available from the combined H2020 and DFG sites and the combined data would include Type I, II and III aneurysms. As the analysis of these additional DFG sites was not originally envisaged or funded in the health economics, it was decided to request that the EU resources originally envisaged in WP3 for the analysis of Registry data be used instead for the analysis of the additional patient data emerging from the DFG sites. By making this amendment, we achieve the same aims as in the GA (health economic analysis of a greater number of patients with a wider range of clinical indications) with the same person-month resources.

### ***Interventions and Comparators***

The intervention is MISACE, followed by open repair or endovascular repair according to the clinician's choice. The standard procedures are open repair or endovascular repair according to the clinician's choice, without MISACE.

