### ***Lifetime cost-utility analysis***

As a secondary analysis, a state transition model will be constructed. This model will consist of a preliminary decision tree to allocate patients into four health states at one year: no complications, permanent hemodialysis, permanent SCI, or dead. Extrapolation beyond one year will then be conducted using the Markov model, assuming that the only transitions will be from the 3 alive states to dead. Discounting will be applied at 3% per year for costs and QALYs.

Using the model, expected survival (given age and gender), cumulative mean costs over that lifetime, and mean QALY (that is, quality adjusted mean survival) will be estimated for each arm in the study.

Likewise, mean lifetime costs, expected survival and HRQOL will be estimated for patients requiring hemodialysis. The rates of mortality, annual costs and HRQOL weights will be based on the literature (7,8).

Individuals with no SCI or permanent hemodialysis will be assumed to have normal rates of mortality and HRQOL for a man or woman of that age (based on population health surveys and official life tables) and no further TAAA-related healthcare costs, other than routine monitoring.

For the lifetime cost-utility analysis, univariate deterministic sensitivity analysis will be conducted by varying key parameters across plausible upper and lower limits. Monte-Carlo simulation will be used to estimate the cost-effectiveness acceptability curve.

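### Both arms mix open and endovascular repair, but neither economic analysis uses the planned repair mode, so the incremental-cost interval carries avoidable graft-price variance and the results cannot be moved to another repair mix

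*Protocol*

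**What the plan says.** Protocol, Background and objectives, sets the question: "The health economic analysis will compare mean costs and QALY outcomes of" MIS²ACE and of standard procedures. Under Interventions and Comparators, the intervention is MIS²ACE "followed by open repair or endovascular repair according to the clinician's choice". For the control arm, "The standard procedures are open repair or endovascular repair according to the clinician's choice, without" MIS²ACE. The two strategies therefore differ only in MIS²ACE, and each contains both repair modes.

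Under Within study economic analysis, "The base-case health economic analysis will be a within-study cost-utility analysis", over one year. The Uncertainty section lists scenarios for EQ-5D tariffs, unit costs and missing-data methods, with bootstrapped intervals and acceptability curves. The Perspective section adds a sensitivity analysis for indirect costs. None of these is by repair mode.

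Of the lifetime model, the Protocol says: "This model will consist of a preliminary decision tree to allocate patients into four health states at one year". The states are free of complications, permanent haemodialysis, permanent SCI and dead. Results are produced by trial arm, and no branch or scenario refers to repair mode.

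On prices, the Unit costs section says: "The exception is the cost of an endovascular stent used in the aneurysm repair, which the German centre estimates may reach 80000" euros, according to how complex the device is. Table 4 prices an open graft at EUR 100-500.

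**The concern.** Repair mode is a large and probably predictable source of cost variation between patients, and the plan leaves it in the error term. Any difference between arms in the share treated endovascularly passes into incremental cost at the price difference between grafts. If the mode was planned before randomisation, that variation could be removed by adjustment; left in, it widens the interval and flattens the acceptability curve.

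The second issue is transfer. A health service with a different balance of open and endovascular repair has one blended cost and QALY difference per horizon, and nothing in the planned output lets it re-weight the result. The trial covers centres in nine countries (Setting & location), so readers with a different mix are to be expected.

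**Working it through.** **Inputs.** Table 4: stent graft EUR 7,395 (Zabrze) or EUR 10,000-80,000 (Leipzig); open graft EUR 100-500, listed only in the Zabrze column; intensive care EUR 886 and ward EUR 448 per day; theatre EUR 5.84 per minute; blood pack EUR 50. Tables 2 and 3: event rates and resource use by mode from the reviewed studies. This document gives no sample size, repair-mode share or SD of cost, so it has no figure to reproduce, and those inputs are assumed below.

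**1. Device gap and its effect on incremental cost.** Shift = (difference between arms in endovascular share) × (stent price − open graft price).

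| Stent (EUR) | Open graft (EUR) | Gap (EUR) | Shift per 5 points (EUR) |
|---|---|---|---|
| 7,395 | 500 | 6,895 | 345 |
| 7,395 | 100 | 7,295 | 365 |
| 10,000 | 500 | 9,500 | 475 |
| 80,000 | 100 | 79,900 | 3,995 |

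The Leipzig rows combine a Leipzig stent price with the Zabrze open-graft price.

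**2. Offsets at the Zabrze stent price.**
- UK Markov study, endovascular minus open: intensive care (2.53 − 3.41) × 886 = −780. Ward −1,770 if intensive-care days are taken out of the stay [(2.64 − 6.59) × 448], or −2,164 if not [(5.17 − 10) × 448]. Theatre (289.72 − 251) × 5.84 = +226. Blood −1,103 ml, or −123 to −221 at an assumed 450 to 250 ml per pack. Net gap about EUR 3,960-4,850.
- French study, stay only: (3.6 − 4) × 886 + (10.3 − 12.2) × 448 = −1,206. Net gap about EUR 5,690-6,090.

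Across both studies, the net shift per 5 points is about EUR 198-304 (0.05 × 3,960 to 0.05 × 6,090).

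**3. Chance imbalance in mix.** Assume 100-250 patients per arm, a 50% endovascular share and no stratification by mode. SD of the difference in share = √(2 × 0.25/n) = 0.071 or 0.045, so the 95% range is ±13.9 or ±8.8 points. At the EUR 6,895 gap this is ±EUR 956 or ±604. At EUR 79,900 it is ±EUR 11,074 or ±7,003.

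**4. What adjustment could gain.** Let D be the gap and S the SD of cost within mode. At a 50% share the variance per patient is S² + 0.25D² unadjusted and S² adjusted, so the ratio of interval widths is S/√(S² + 0.25D²). For S = 0.5D, D and 2D (assumed) the ratio is 0.707, 0.894 and 0.970: intervals 29%, 11% and 3% narrower. Rare, very costly SCI cases raise S, and then the gain at the lower price gap is small.

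**5. Complications by mode (Table 2, endovascular minus open, percentage points).** SCI +3.1 and −5.2 in two studies; 30-day mortality −11.4, +1.3 and −7.0 in three; one-year mortality +10.1 and permanent haemodialysis −11.6 in one each. SCI and 30-day mortality conflict in sign. A 10-point difference in mix would move SCI by +0.3 or −0.5 points. An assumed MIS²ACE risk ratio of 0.3-0.7 at a 50:50 mix would lower it by 0.8-1.8 points (pooled risk 2.55%) or 3.9-9.2 points (pooled risk 13.1%).

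**6. Transfer to another mix.** Suppose MIS²ACE halves SCI in both modes (assumed). The absolute reduction is then 2.05 points endovascular against 0.5 open on the French rates, and 5.25 against 7.85 on the US rates. Even a constant relative effect gives an absolute benefit that depends on the mix, in a direction the literature does not settle.

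**The case against.** The strongest objection is that pooling is deliberate. Both strategies leave mode to the clinician, and the randomised contrast estimates the effect of adding MIS²ACE to usual practice. That stands. A reader might infer that the pooled result answers no real decision; the documents do not support this, because it answers the declared question at the trial's mix.

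Nor is imbalance in mode bias. If mode is fixed before randomisation, imbalance is sampling error within the bootstrap interval. If it is chosen afterwards and MIS²ACE influences it, the resulting cost belongs to the strategy. The document does not say which applies. This also stands, and it is why only the planned mode is suitable as a covariate.

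A reader might also infer that mode drives complications far more than MIS²ACE does. Table 2 does not show it: signs conflict for SCI and 30-day mortality, the Protocol calls the populations heterogeneous, and the trial's hypothesis is that MIS²ACE "can greatly reduce the incidence of ischaemic spinal cord injury (SCI) and mortality compared to standard open surgical or endovascular thoracoabdominal aneurysm repair alone". Likewise, coil price is not the cost of the whole MIS²ACE procedure, so graft price cannot be said to outweigh it.

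The upper cost figures are ceilings. EUR 80,000 is a price a graft may reach, and the cited scoping review gives a median of USD 17,272 (interquartile range 8,683-27,931) for graft and other central supplies. The planned unit-cost scenarios vary the price but leave the mix untouched.

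Finally, stratification or subgroups by mode may be set in the clinical trial protocol or statistical analysis plan, which are not at hand. If randomisation was stratified by planned mode, the ranges in step 3 largely disappear. An unadjusted, unstratified bootstrap would then overstate the uncertainty, so adjustment would still be worth stating.

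**Conclusion.** The point holds as a limited improvement, not as an error in the pooled comparison. The stated one-year and lifetime analyses ignore repair mode, while the plan's own prices differ by EUR 6,895 to 79,900 between modes on device price alone. A 5-point difference in endovascular share moves incremental cost by about EUR 345 to 3,995, or by about EUR 198 to 304 at the Zabrze price after the offsets in step 2. The top figures rest on a ceiling price and on stent and open-graft prices from different centres.

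The precision to be gained depends on the within-mode SD of cost, which is not given: about 3% to 29% narrower intervals over the assumed range. The loss of transferability does not depend on those assumptions, because no planned output is by mode.

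**What to change.** 1. **Interventions and Comparators:** state whether repair mode is planned and recorded before randomisation.
2. **Uncertainty and Missing data:** if it was recorded then, estimate incremental cost and incremental QALYs with planned mode as a covariate, fitted within each bootstrap sample, and include it in the imputation model. Do not use the mode performed, which the arm may affect.
3. **Within study economic analysis:** keep the single estimate over all patients as base case. Report incremental cost, QALYs and acceptability curves for planned open and planned endovascular repair as a secondary, descriptive analysis.
4. **Lifetime cost-utility analysis:** add a scenario that varies the repair mix and the mode-specific baseline risks. Separate event probabilities in every arm-by-mode cell need not be required: with an assumed 100 patients per arm, half of them open, the French 1% SCI rate gives 50 × 0.01 = 0.5 expected events in a cell.

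The cost is a few sentences of plan wording and modest extra analysis, with no new data if planned mode is already on record. The downside is wide mode-specific intervals and sparse events, so those results should carry no formal conclusion. If planned mode was not recorded before randomisation, items 2 and 3 cannot be done cleanly and only the model scenario remains.
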